8.3.9 Overdose

An overdose is defined as the accidental or intentional ingestion or infusing of any dose of study treatment that exceeds the dose described in the protocol. Overdoses are not considered AEs; however, all overdoses should be reported to the study PI and Multicenter Project Management Office. An overdose should be reported even if it does not result in an AE. Overdoses do not need to be recorded on the eCRF; dosing information is recorded on the dose administration eCRF. If the overdose results in an AE, the AE must also be recorded as an AE. An overdose does not automatically make an AE serious, but if the consequences of the overdose are serious, for example death or hospitalization, the event is serious and must be recorded and reported as an SAE.

Deaths	
Any reportable death while on study or within 30 days of study	Immediately, within 24 hours, to PI, Georgetown Multicenter Project Management Office, ERYTECH (SUSAR , suspected unexpected serious adverse reactions, ONLY), and to the IRB (Per local IRB policy)
Any reportable death while off study	Immediately, within 24 hours, to PI, Georgetown Multicenter Project Management Office, ERYTECH (SUSAR ONLY), and to the IRB (Per local IRB policy)
Adverse Events/Unanticipated Problems	
Any reportable adverse events/unanticipated problems as described in Sections 8.3.2, 8.3.4 and 8.3.5 (other than death)	Immediately, within 24 hours to PI, Georgetown Multicenter Project Management Office, and ERYTECH

Table 5: The timeframe for reporting Adverse Events/Unanticipated Problems

	(SUSAR ONLY), Within 7 calendar days (or within local IRB guidelines) to the IRB, and Within 7 or 15 calendar days to the FDA, as required
All adverse events regardless of grade and attribution should be submitted cumulatively	Entered into CRFs and Include in DSMC reports

Erytech Reporting:

Sites will report events/problems to the PI, [name] and the Georgetown Multicenter Project Management office and the Georgetown Multicenter Project Management Office will submit information as required to Erytech.

Email:

9 Study Drugs and Treatment Plan

9.1 Study Drugs Description

9.1.1 Eryaspase

Eryaspase is a dispersion for infusion of allogeneic erythrocytes encapsulating recombinant *E. coli* L asparaginase, in a saline preservative solution. Eryaspase is an off-shelf investigational agent. Eryaspase is produced for each individual patient taking into account blood group and phenotype and dose of ASNase appropriate for body weight.

Eryaspase was previously studied as a single agent in twelve patients with pancreatic cancer. No patient experienced dose limiting toxicities at any dose level. One patient experienced grade 3 lymphopenia one patient experienced grade 1 allergic pruritus. Eryaspase was later studied in combination with chemotherapy in 93 patients with pancreatic cancer, in comparison to the control arm of chemo alone grade 3 and 4 hematological adverse event occurred with similar frequency between treatment arms. The most common adverse events were asthenia (68.8%), nausea (62.4%, anemia (45.2%), thrombocytopenia (43%), emesis (44.1%), abdominal pain (35.5%) and diarrhea (39.8%), however these are most likely secondary to chemotherapy²⁶.

In previous studies of Eryaspase in acute lymphocytic leukemia the most common adverse events were thrombocytopenia (13.6%), elevated transaminases (13.6%), anemia (8.8%), neutropenia (6.4%), and leukopenia (5.6%)²⁶.

Further information can be found in the current version of the Eryaspase Investigator's Brochure.

9.1.2 FOLFIRINOX (5-FU, Leucovorin, Irinotecan, and Oxaliplatin)

5-FU is an antineoplastic antimetabolite agent. It is commercially available as an injectable solution for IV use. 5-FU will be administered as per institutional procedure.

Leucovorin is folinic acid (the active metabolite of folic acid). It is an essential coenzyme for nucleic acid synthesis and is used to enhance the cytotoxicity of 5-FU. It is commercially available as a powder for reconstitution for IV use. Leucovorin will be administered as per institutional procedure.

Irinotecan is an antineoplastic agent of the topoisomerase I inhibitor class. It is commercially available as an aqueous solution intended for dilution prior to IV infusion. Irinotecan will be reconstituted/used as per the manufacturer's suggestions and will be administered as per institutional procedure.

Oxaliplatin an antineoplastic antimetabolite agent. It is commercially available as an injectable solution for IV use. Oxaliplatin will be administered as per institutional procedure.

9.2 Study Drugs Dosing

9.2.1 Eryaspase

At the treatment initiation, Eryaspase will be prepared and dispatched after all screening assessments have been completed and the results reviewed and after it has been confirmed that the patient meets all eligibility criteria. The dose of Eryaspase will follow the dose escalation schema. Eryaspase is administered over approximately 60 minutes per bag, depending on the volume of the bag(s). The entire content of each bag is to be administered unless otherwise specified. Eryaspase administration must be completed before the expiry time clearly stated on the label of the Eryaspase bag. Date of administration, exact start and end times of infusion, and volume administered will be recorded on the Shipment and Administration Form (SAF) as described in the Investigational Medicinal Product (IMP) Manual. A \pm 1-day window is permitted for Eryaspase dosing for scheduling purposes.

Detailed instructions related to Eryaspase administration and contact information in case of any issues are provided in the IMP Manual.

9.2.2 FOLFIRINOX (5-FU, Leucovorin, Irinotecan, and Oxaliplatin)

- 5-fluorouracil 2400 mg/m² continuous infusion over 46 hours
- Oxaliplatin 85 mg/m² (Intravenous infusion)
- Irinotecan 150 mg/m² (Intravenous infusion)
- Leucovorin 400 mg/m2 (Intravenous infusion)

Institutional guidelines should be followed for the administration of FOLFIRINOX. It is recommended the administration be as follows:

- 1. Oxaliplatin is administered first over 2 hours,
- 2. Leucovorin over 2 hours (30 minutes prior to Irinotecan),
- 3. Irinotecan over 1.5 hours.

9.3 Other Medication & Supportive Care

9.3.1 Antiemetic Therapy

Given the high incidences of nausea and vomiting associated with the FOLFIRINOX regimen, a combination of aprepitant, 5-HT3 antagonist, and dexamethasone before chemotherapy is strongly recommended.

9.3.2 Irinotecan-induced cholinergic syndrome

Atropine 0.25-1.0 mg IV may be given prior, during, or after infusion of irinotecan for irinotecan-induced cholinergic symptoms including lacrimation, rhinorrhea, diaphoresis, flushing, abdominal cramps, diarrhea, etc.

9.3.3 Growth Factor Support

Indications for use of GCSF should follow American Society for Cooperative Oncology (ASCO) guidelines. The choice of G-CSF support (filgrastim vs. pegfilgrastim) is at the discretion of the treating physician. Use of the erythropoiesis-stimulating agent is not allowed. It is strongly recommended that patients over the age of 65 receive growth factor support following initiation of treatment.

9.3.4 Transfusion of blood products

Transfusions are permitted. However, transfusion of fresh frozen plasma should be minimized, as it provides an exogenous source of asparagine. It is preferable to administer antithrombin III (AT III) concentrates in case of a decrease in AT III following Eryaspase administration. Hemoglobin must be ≥ 9 g/dL at Cycle 1 Day 1 and must be ≥ 8 g/dL before all subsequent doses. If hemoglobin is <8 g/dL, then appropriate measures must be taken according to standard clinical practice prior to further administration of chemotherapy.

9.3.5 Systemic and inhaled steroid treatment

A standard 3- to 5-day course of dexamethasone following the institutional standard of care is permitted for the prevention of treatment-induced nausea and vomiting. In addition, oral glucocorticoids at a daily dose of 1.5 mg dexamethasone (or equivalent) are permitted.

9.3.6 Antidiarrheal medications

Patients should be closely monitored for diarrhea. Dose modification is allowed for diarrhea. Patients should be instructed to take loperamide at the first sign of poorly formed or loose stools. Patients should take loperamide in the following fashion: 4 mg at the first onset of diarrhea, then 2 mg every 2 hours until diarrhea resolved. The total dose of loperamide should not exceed 16 mg/day. Patients are instructed to notify their treating physicians if diarrhea is not resolved within 24 hours. Additional antidiarrheal medications including Lomotil, tincture of opium, or octreotide can be used.

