5.5 Dose Limiting Toxicities (DLT)

To the extent possible, any adverse events that are deemed to study drug-related and are ongoing at end of treatment will be followed up to resolution or until a determination is made that the unresolved event is stable.

In general, Grade 1 and 2 toxicities do not require any dose modification for any of the chemotherapy agents or for Eryaspase. However, appropriate supportive care will be provided for the management of drug-related toxicities.

Hematologic DLT is defined as any of the following that occurs during the first cycle (total of approximately 28 days) of treatment that is attributed as possibly, probably, or definitely related to Eryaspase alone or the combination of Eryaspase and FOLFIRINOX:

- Grade 4 neutrophil count decrease > 7 day duration
- Febrile neutropenia \geq Grade 3 of any duration
- Grade 3 or Grade 4 platelet count decrease
- Any Grade 4 platelet count decrease with bleeding

Non-hematologic DLT is defined as any grade 3 or grade 4 adverse event, based on NCI CTCAE that occurs during the first cycle (total of approximately 28 days) of treatment that is considered possibly, probably, or definitely related to Eryaspase alone or the combination of Eryaspase and FOLFIRINOX with the following specific exceptions:

- Grade 3 or 4 AST, ALT, alkaline phosphatase, or total bilirubin due to biliary obstruction or infection
- Grade 3 or 4 nausea, vomiting, or diarrhea resolved with maximal supportive care within 7 days
- Grade 3 mucositis resolved with supportive care
- Grade 3 fatigue lasting less than 7 days
- Grade 3 or 4 laboratory abnormalities that are not clinically significant or do not require any clinical intervention.

Any treatment-related toxicity that results in treatment delay for > 21 days cumulatively during the first cycle or > 14 days cumulatively during the second cycle will be considered a DLT, and the patient will be removed from the study. If the treatment delay during the first cycle is due to reasons other than treatment-related toxicity, the patient will be replaced as the subject will be considered to be inevaluable for DLT.

5.6 **Dose modification**

Dose reduction or modification are only allowed after passing the 28 days DLT period. Recommended mFOLFIRINOX dose modifications are listed in Table 3, however modification may follow investigator or institutional guidelines. Modifications may be made to any or all chemotherapy agents, per investigator discretion.

Table 3

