D Diarrhea		Patients should be instructed in the use of loperamide as treatment for diarrhea. Patient should not be retreated with irinotecan until recovery from diarrhea, without loperamide for at least 24 hours, has occurred
Toxicity Grade		
2	Consider holding, but can treat per Investigator discretion.	
	1st occurrenc	e: Reduce irinotecan by 1 dose level
3-4	2nd occurrent FU dose by 1	ce: Reduce oxaliplatin dose by 1 dose level and 5- dose level
	3rd occurrenc	e: Discontinue all protocol treatment

Table 4E

E Mucositis			
Toxicity Grade	5-F	FU	Oxaliplatin
2	Hold tre	eatment	Hold treatment
	until resolution	n to ≤ Grade 1,	until resolution to ≤ Grade 1,
	Continue at sa	ame dose level	Continue at same dose level
3-4	Hold tre	eatment	Hold treatment
	until resolution	n to ≤ Grade 1,	until resolution to ≤ Grade 1,
	Continue at ne	ext lower dose	Continue at next lowest dose
	lev	vel	level

Table 4F

F Oxaliplatin related neuropathy		Paresthesia or peripheral sensory neuropathy	
Toxicity Grade	Duration of toxicity 1–7 days	Duration of toxicity more than 7 day	Persistent (duration of toxicity more than 14 days)
2	No dose modification	No dose modification	Next lowest dose level for oxaliplatin
3	Next lowest dose level for oxaliplatin	Next lowest dose level for oxaliplatin	Discontinue
4	Discontinue	Discontinue	Discontinue

Table 4G

G		
Palmar-plantar erythrodysesthesia syndrome		
Toxicity Grade 2	Consider holding	, but can treat per Investigator discretion.
Toxicity Grade 3-4	Rec	luce 5–5-FU by 1 dose level

5.7 Discontinuation of Eryaspase

- DLT during dose escalation
- Study completion
- Patient withdraws from the study for any reason, including withdraws consent.
- Progressive disease
- Declared discontinuation due to missed Eryaspase doses.

5.8 Duration of therapy

If at any time the constraints of this protocol are considered to be detrimental to the patient's health and/or the patient no longer wishes to continue protocol therapy, the protocol therapy should be discontinued and the reason(s) for discontinuation documented in the case report forms.

Version 2.1, 16 March 2022

In the absence of treatment delays due to adverse events, treatment may continue for a total of 12 treatments of FOLFIRINOX (approximately 6 months) or until one of the following criteria applies:

- Documented and confirmed disease progression
- Death

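### The loperamide schedule in Section 9.3.6 reaches its own 16 mg/day limit at hour 12, the only stated notification point is hour 24, and no text says which sentence governs in between.

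*Combined protocol and SAP*

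**What the plan says.** Section 9.3.6 addresses medication that the patient takes on noticing loose stools. It contains three statements that bear on each other, the first two in adjacent sentences:

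- Schedule and limit: a first dose of 4 mg at onset, "then 2 mg every 2 hours until diarrhea resolved. The total dose of loperamide should not exceed 16 mg/day".
- Notification: "Patients are instructed to notify their treating physicians if diarrhea is not resolved within 24 hours".

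The same paragraph opens by asking for close monitoring and ends with: "Additional antidiarrheal medications including Lomotil, tincture of opium, or octreotide can be used". Section 9.3.7 lets investigators prescribe whatever supportive care they judge necessary.

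The only other loperamide text is Table 4D in Section 5.6. It says "Patients should be instructed in the use of loperamide as treatment for diarrhea" and sets a loperamide-free period before irinotecan is resumed. It gives no schedule, no daily limit and no rule for a patient who has reached the limit.

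**The concern.** The only stop condition in the dosing sentence is resolution. The next sentence sets a ceiling that this schedule reaches well before the time at which the patient is told to notify the physician. A patient whose diarrhea persists must either keep to the interval and pass the ceiling, or keep to the ceiling and abandon the interval. The text does not say which, and it does not say what to do in the second case before hour 24.

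At stake is whether a patient can follow the instruction as written, and whether sites explain it in the same way. The regimen contains irinotecan, and the protocol gives diarrhea its own dose-modification table, so the instruction is likely to be used.

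**Working it through.** **Inputs, all from Section 9.3.6.** First dose 4 mg at onset (hour 0); then 2 mg every 2 hours until resolution; limit 16 mg per day; notification at 24 hours without resolution. The length or start of a *day* is not defined.

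**Reading 1: the day is the 24 hours from onset**, the same clock as the notification sentence.

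Cumulative dose after the dose at hour *t* (*t* = 0, 2, 4, ...): D(t) = 4 + 2 × (t/2) mg.

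| Hour | 0 | 2 | 4 | 6 | 8 | 10 | 12 | 14 | 22 |
|---|---|---|---|---|---|---|---|---|---|
| Total, mg | 4 | 6 | 8 | 10 | 12 | 14 | 16 | 18 | 26 |

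- Limit reached: 4 + 2 × 6 = 16 mg at hour 12.
- First dose over the limit: hour 14, total 18 mg.
- First 24 hours at the stated interval: 4 + 2 × 11 = 26 mg, with the last dose at hour 22. That is 10 mg over the limit (26/16 = 1.625, or about 63% above it).
- Any later full day at the stated interval: 12 × 2 = 24 mg, which is 8 mg over (24/16 = 1.5).
- If the limit is kept instead, the doses at hours 14, 16, 18, 20 and 22 are withheld. The time from the last dose to the notification point is 24 − 12 = 12 hours.

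So the stated maximum of 16 mg/day is not reproduced by running the stated schedule for a day.

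**Reading 2: the day is a calendar day.** The limit then resets at midnight, and the result depends on the clock time of onset. Keeping to 16 mg in each calendar day:

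| Onset | Doses withheld in first 24 h | Taken in first 24 h, mg |
|---|---|---|
| 00:00 | 5 | 16 |
| 02:00 | 4 | 18 |
| 04:00 | 3 | 20 |
| 06:00 | 2 | 22 |
| 08:00 | 1 | 24 |
| 10:00 to 16:00 | 0 | 26 |
| 18:00 | 1 | 24 |
| 20:00 | 2 | 22 |
| 22:00 | 3 | 20 |

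The interval without loperamide before the notification point now runs from none to 12 hours, the longest being for onset at midnight. Where no dose is withheld, the patient takes 26 mg within 24 hours of onset. A later full calendar day at the stated interval is still 24 mg against 16 mg. The calendar reading moves the conflict but does not remove it.

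**The case against.** The strongest reply is that a schedule followed directly by a maximum is ordinarily read with the maximum in control. On that reading nobody is directed to take 26 mg, and what is left is a missing bridging instruction. This largely stands. A reader might infer that the protocol tells patients to exceed its own limit; it does not, because the limit is explicit. But the dosing sentence names only resolution as its end, no text gives the limit precedence, and if the limit does govern, the unaddressed interval is the result.

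Other stronger readings also fail on the documents:

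- *The patient may not call before 24 hours.* The text states one notification point and does not discourage an earlier call.
- *The patient is without care for 12 hours.* Close monitoring is requested, other antidiarrheals are allowed, and Section 9.3.7 permits further supportive care. The gap is that none of these is tied to reaching the limit. Twelve hours is also a maximum under the calendar-day reading.
- *The daily total is 28 mg.* That counts the hour-24 dose, which opens the next 24-hour period.
- *DLT status would differ between patients.* Section 5.5 exempts "Grade 3 or 4 nausea, vomiting, or diarrhea resolved with maximal supportive care within 7 days". Nothing shows that up to 12 hours without loperamide on the first day alters resolution within 7 days, or that first-day loperamide alone is the maximal care meant.
- *The 39.8% diarrhea rate in Section 9.1.1 measures exposure to the problem.* It comes from Eryaspase with other chemotherapy; Section 3.3 says 90% of patients in that trial received gemcitabine. It is not a rate for this regimen.

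Finally, any patient handout is not among the documents, so it cannot be judged whether patients receive fuller instructions. The text also does not say where the patient takes the drug.

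**Conclusion.** The inconsistency is real and minor. For diarrhea lasting beyond 12 hours, on the 24-hour reading, the stated interval and the 16 mg/day limit cannot both be followed: 26 mg in the first 24 hours, then 24 mg per full day. If the limit governs, loperamide ends up to 12 hours before the only stated notification point, or 0 to 12 hours before it if the day is a calendar day.

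The figures assume that doses are taken at every 2-hour point, including overnight, and that diarrhea continues throughout. A patient whose diarrhea resolves earlier, or who misses doses, may never meet the conflict. The later-day figure applies only after the notification point has passed.

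This is a patient-safety wording defect in one supportive-care paragraph. No effect on DLT classification, dose escalation or sample size is shown, and none is claimed.

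**What to change.** In Section 9.3.6, reconcile the schedule, the daily limit and the notification sentence so that one patient can follow all three. State which governs when they conflict, and define what a day means for the limit. Use the same text in any patient instructions. The dose, interval, limit and notification rule are for the sponsor's clinical team to decide; this point asks only that the sentences agree and does not ask for a new contact trigger.

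The cost is a sentence or two in a protocol amendment, with a matching change to any patient material. No design, sample-size or analysis text needs to change.

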9.3.7 Permitted Concomitant Medications

Investigators may prescribe concomitant medications or treatments deemed necessary to provide adequate prophylactic or supportive care.

9.4 Ervaspase Acquisition, Accountability, Preparation, Storage, and Handling

9.4.1 Acquisition

Eryaspase will be dispatched directly to each site only after receipt of the required information in accordance with ERYTECH procedures.

Information to be provided at study start: Erythrocytes phenotype (including D, C, E, c, e, and K antigens), ABO blood group status, and Rhesus factor, all assessed on 2 separate samples, which can be collected on the same day. In addition, results of an irregular antibody screening test (IAST) are required. This information is required at least 5 working days before the first Eryaspase infusion. For group A and AB patients, sub-grouping A1/A1B and A2/A2B is required. If A subgroup, screening of anti-A1 antibodies (Indirect Coombs method) should be performed for A2 and A2B patients. The A2 and A2B patients will require anti-A1 antibodies screening before each administration along with IAST and documented on IAST form.

Information to be provided during the treatment phase: Results of IAST performed less than 3 days prior to each Eryaspase infusion.

A prescription form indicating patient identifiers and body weight should be provided at the latest 5 working days prior to each Eryaspase infusion.

The following information is required before Eryaspase can be shipped to the site:

- The name and contact details of the recipient, who should be the Investigator or designee.
- The location for delivery (local pharmacy or blood bank).

Detailed instructions for completing and providing the phenotype, blood group, and Rhesus factor information, the IAST results, and the prescription form are provided in the IMP manual. Eryaspase will be shipped to the Investigator in a qualified container by a specialized carrier who will ensure that the cold chain is maintained between +2-8°C (35-46°F).

If a temperature excursion outside the range of $+2^{\circ}$ C to $+8^{\circ}$ C (35-46°F) occurs, the product should be quarantined and ERYTECH Pharma should be contacted to determine the usability of the product. Refer to the IMP manual for ERYTECH contact information.

If it is not used immediately after receipt, it is mandatory that Eryaspase be stored at temperatures between +2 and +8°C (35-46°F).

Eryaspase may be stored at room temperature for up to 6 hours prior to administration, including infusion time; it must not be stored at room temperature for more than 6 hours.

9.4.2 Accountability

The Investigator or designee is responsible for IMP accountability, reconciliation, and record maintenance (i.e., records of receipt, reconciliation, and final disposition). Further guidance and information concerning the final disposition of unused IMP are provided in the IMP Manual.

